1.0 STATISTICAL DESIGN AND ANALYSES FOR 0076-ot

1.1 General Design

1.1.1 Study Hypothesis

A web-based EMR-integrated point-of-care CDS tool for OUD is both feasible and usable in the primary care setting.

1.2 Primary and Secondary Outcomes (Endpoints)

Primary Aims:

- 1) To program an OUD-CDS tool based on a NIDA-Blending Initiative white paper “Clinical Decision Support for Opioid Use Disorders: Working Group Report” and national guidelines (VA (VA 2015), ASAM (ASAM 2015)) for use in an EMR.

Measure 1. Demonstrate that the OUD-CDS is functional and accurate through:

- a) Testing in the EMR test environment,
 - b) Chart audit validation of CDS output, and
 - c) Approval of the tool by specialty addiction physician and PCP pilot testers prior to the full rollout.
- 2) To descriptively analyze PCP acceptability, satisfaction and use rates high enough to demonstrate proof of concept

Measure 2A. By the end of the 6-month pilot intervention, the monthly PCP use rate of the CDS for targeted high-risk patient encounters for PCPs with CDS access will be >60%.

Measure 2B. By the end of the 6-month pilot intervention, >60% of PCPs with CDS access will report feeling confident in assessing and treating OUD

Measure 2C. At the end of the 6-month pilot intervention, >80% of PCPs with CDS access will rate the OUD-CDS ≥ 4 on a 5-point Likert scale of likeliness to recommend use of the tool to their colleagues.

Secondary Aims. We will examine the usefulness of the OUD-CDS tool by comparing pre- and post-intervention rates of screening for OUD in high-risk patients, TAPS use, OUD diagnosis, use of medication-assisted therapy, as well as treatment referral patterns, for 3 groups of PCPs: (1) those with CDS access and buprenorphine certification, (2) PCPs with CDS access but without buprenorphine certification, and (3) PCPs without CDS access.

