2.0 RECRUITMENT

PCPs will be voluntarily recruited from HPMG and PNMG in person and via emailed invitations. We will recruit all PCPs who have or will soon have buprenorphine waivers, as they will be able to use the entirety of the OUD-CDS tool. In our invitation to participate in the study, we will inform PCPs that they will receive \$150 (PCPs without CDS access) or \$300 (PCPs with CDS access) each to compensate them for their time in completing emailed surveys at the beginning and end of the 6-month pilot intervention phase (all PCPs), and for their time in submitting feedback via the feedback tab in the CDS (PCPs with access to the CDS).

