3.0 RANDOMIZATION AND FACTORS FOR STRATIFICATION

PCPs who are recruited and are buprenorphine-certified will be placed into the group of PCPs who have OUD-CDS access. PCPs who are recruited and do not have buprenorphine certification will be randomized to receive or not receive access to the OUD-CDS. We will be aware of practice location, patient panel size and number of patients for whom the CDS-OUD was triggered and can analyze results based on individual practice location or panel, but given the small nature of this pilot project we do not anticipate statistically meaningful information from these factors.

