4.1.2 Projected Number of Participants per Site

We anticipate 37-43 PCPs from approximately twenty primary care clinics will participate.

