4.3 Significance Testing

This pilot study for OUD-CDS feasibility and usability does not entail statistical testing or power calculations. Provider characteristics, patient characteristics, and OUD-CDS use rates will be tracked and described.

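### Does splitting only the CDS-access groups by buprenorphine certification bias the comparison of medication-assisted therapy?

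*SAP*

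**What the plan says.** Three sections of the SAP bear on this.

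- **Section 1.2, Secondary Aims**, sets out the comparison. It looks at rates before and after the intervention for several outcomes, among them "use of medication-assisted therapy, as well as treatment referral patterns, for 3 groups of PCPs". The groups are "1) those with CDS access and buprenorphine certification, (2) PCPs with CDS access but without buprenorphine certification, and (3) PCPs without CDS access".
- **Section 2.0** describes recruitment: "We will recruit all PCPs who have or will soon have buprenorphine waivers, as they will be able to use the entirety" of the tool. The same section sets a payment for PCPs who have no access to the tool, so it does not promise access to everyone recruited.
- **Section 3.0** describes allocation by two routes. Certified PCPs are not randomized: "PCPs who are recruited and are buprenorphine-certified will be placed into the group of PCPs who have OUD-CDS access". For the rest, "PCPs who are recruited and do not have buprenorphine certification will be randomized to receive or not receive access to the OUD-CDS". No allocation ratio is given.

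No section gives the date at which certification is read for the analysis groups, or says how a PCP who certifies during the 6 months is classed. Section 4.1.2 gives the size of the study, "We anticipate 37-43 PCPs from approximately twenty primary care clinics will participate", without a breakdown by group. Section 4.3 says the study "does not entail statistical testing or power calculations".

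**The concern.** The group definitions look lopsided. Certification separates group 1 from group 2, but group 3 is defined only by lack of access. Because section 2.0 deliberately recruits PCPs whose waiver is still to come, some changes of status during the pilot are to be expected.

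Suppose certification means status at the time of analysis. A PCP randomized to the tool who then certifies fits the description of group 1 and drops out of group 2. A PCP randomized to no tool who certifies stays in group 3. Newly certified PCPs are then removed from one randomized arm only, after randomization. Section 2.0 ties the waiver to use of the whole tool, so certification is plausibly related to MAT use, and group 2 would lose the PCPs most likely to use it. Groups 2 and 3 are the only randomized contrast in the study, and the distortion would run against the tool. Group 1, which is not randomized, would also take in some randomized PCPs.

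Sections 2.0 and 3.0 also seem to pull apart. The first recruits PCPs expecting a waiver because they can use the whole tool; the second, read literally, randomizes those not yet certified, so some of them get no tool.

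**Working it through.** The SAP has no figure of its own to reproduce. The check sets the sections side by side, then works through the alternative reading.

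**Step 1. Allocation against analysis groups.**

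| Outcome of allocation (section 3.0) | Group (section 1.2) |
|---|---|
| Certified, given access | 1 |
| Not certified, randomized to access | 2 |
| Not certified, randomized to no access | 3 |

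The match is one to one. Group 3 needs no split, because under section 3.0 nobody certified at allocation can be in it. With certification read at allocation, groups 2 and 3 are the two randomized arms, complete.

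**Step 2. PCPs expecting a waiver.** If the waiver arrives before allocation, the PCP is certified under section 3.0 and enters group 1. If not, the PCP is randomized and enters group 2 or 3. Both cases are covered. Placing such a PCP directly in the access group without certification is something section 3.0 does not provide for.

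**Step 3. Size under each reading, with a true tool effect of zero.** All inputs are assumed. Let q be the share of each randomized arm that certifies later, pc the MAT rate under certified PCPs and pu the rate under uncertified PCPs.

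- Group 3 rate: q·pc + (1 − q)·pu.
- Group 2 rate with status taken at allocation: the same. Difference (group 2 minus group 3): 0 for every q.
- Group 2 rate with current status: pu. Difference: −q·(pc − pu).

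Take 11 PCPs per arm with equal panels, pc = 30% and pu = 5%:

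| Certifying later, per arm | Group 3 | Group 2, current status | Difference |
|---|---|---|---|
| 1 | (1×30 + 10×5)/11 = 7.3% | 5.0% | −2.3 points |
| 2 | (2×30 + 9×5)/11 = 9.5% | 5.0% | −4.5 points |
| 3 | (3×30 + 8×5)/11 = 11.8% | 5.0% | −6.8 points |

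Over a wider range, with (pc, pu) from (10%, 0%) to (50%, 5%), the difference is −1.0 to −4.5 points at q = 0.1 and −5 to −22.5 points at q = 0.5. At q = 0 it is 0.

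**Step 4. Does the pre-post design remove it?** Not under the current-status reading. If every randomized PCP starts at pu, the change is 0 in group 2 and q·(pc − pu) in group 3, and the difference in change is again −q·(pc − pu). What removes the bias is reading certification at allocation.

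**The case for a change.** The strongest case for a change is that the wording in section 1.2 carries no date, so current status is a possible reading, and an analyst would choose between the readings with data in hand. Recruitment makes changes of status likely. With 37 to 43 PCPs in all, a few of them changing group could visibly move a group rate. The absence of a test does not protect against bias, since the difference would still be described as evidence of usefulness. Writing the date down would cost a sentence or two and one recorded date per PCP.

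Part of this stands. The date is indeed missing, the arithmetic is right on its assumptions, and the bias would be one-sided if current status were used.

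The rest does not. Moving a PCP from group 2 to group 1 on certification is a rule that the SAP states nowhere; it has to be supplied. The one place where certification has a function is allocation, and that use yields exactly the groups listed. Sections 2.0 and 3.0 do not truly conflict: one says who is invited, the other how those who join are allocated. How many PCPs expecting a waiver would go without the tool cannot be stated, because no ratio is given. Nor can the size of any bias be derived, since q, pc, pu and the arm sizes are all absent from the SAP.

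**Conclusion.** No change follows. The missing date for certification status is a gap that an analyst fills sensibly from section 3.0: status at allocation, with groups 2 and 3 kept as randomized. On that reading the bias from this source is zero, however many PCPs certify later.

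The figures of −2.3 to −6.8 points describe a different analysis, which the SAP does not prescribe, and rest wholly on assumed inputs.

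The reach is also limited. The comparison belongs to a secondary aim of a descriptive pilot without significance testing. None of the primary measures in section 1.2 uses the certification split; measures 2A to 2C refer to all PCPs with access taken together.

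This conclusion assumes that allocation follows section 3.0 as written and that certification is read when allocation is made. Stating the date would put the natural reading in writing without altering the analysis.

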2.0 RECRUITMENT

PCPs will be voluntarily recruited from HPMG and PNMG in person and via emailed invitations. We will recruit all PCPs who have or will soon have buprenorphine waivers, as they will be able to use the entirety of the OUD-CDS tool. In our invitation to participate in the study, we will inform PCPs that they will receive \$150 (PCPs without CDS access) or \$300 (PCPs with CDS access) each to compensate them for their time in completing emailed surveys at the beginning and end of the 6-month pilot intervention phase (all PCPs), and for their time in submitting feedback via the feedback tab in the CDS (PCPs with access to the CDS).

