4.1 Rationale for Sample Size and Statistical Power

4.1.1 Projected Number of Sites

This study will occur at PNMG and HPMG, both of which are divisions of HealthPartners. This pilot intervention will occur at primary care clinics at which one or more eligible PCPs have consented to participate. We anticipate a total of 37-43 PCPs from twenty primary care clinics will participate.

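### The pre/post change in MAT use and referral can mix a newly gained waiver with the tool, because PCPs about to be waivered are recruited and not described separately

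*SAP*

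**What the plan says.** Three places in the SAP bear on this.

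- **Section 2.0 (Recruitment)** takes in PCPs who do not yet hold a waiver but expect one: "We will recruit all PCPs who have or will soon have buprenorphine waivers". The reason given is that the whole tool is then open to them.
- **Section 3.0 (Randomization)** assigns by certification status. On one side, "PCPs who are recruited and are buprenorphine-certified will be placed into the group of PCPs who have OUD-CDS access". On the other, "PCPs who are recruited and do not have buprenorphine certification will be randomized to receive or not receive access to the OUD-CDS". It does not mention PCPs whose waiver is pending.
- **Section 1.2 (Secondary Aims)** examines usefulness by "comparing pre- and post-intervention rates of screening for OUD in high-risk patients, TAPS use, OUD diagnosis, use of medication-assisted therapy", together with referral patterns, in three groups. The first is "1) those with CDS access and buprenorphine certification"; the second has access without certification; the third has no access.

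The SAP does not say when certification is determined for grouping, or how a waiver gained in the pre- or post-intervention period is handled in the description. Sections 4.2 to 4.4 make all analyses descriptive.

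**The concern.** Someone about to receive a waiver has, by definition, spent the time before recruitment without one. If that PCP is later counted as certified with access, two things change between the pre and post periods: the PCP can now prescribe under the waiver, and the PCP has the tool. MAT use and referral are the two listed outcomes that a waiver could plausibly move by itself.

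The design cannot separate the two. Every certified recruit gets access, so no certified group without access shows what a new waiver does alone. Groups 2 and 3 do not fill that gap, because neither is a certified comparison.

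At stake is the reading of the group 1 change in MAT use and referral. Group 1 can use the whole tool, so readers will look to its MAT change first when they ask whether the tool was useful.

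**Working it through.** The SAP gives no figure on this point, so there is nothing to reproduce. The check has two parts.

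**1. Where a PCP with a pending waiver ends up**

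| Reading | Basis | Where the mixing falls |
|---|---|---|
| Counted in group 1 once certified | Section 2.0's reason for recruiting them is use of the whole tool | Group 1 pre/post change |
| Certified between recruitment and assignment | Section 3.0 places them with access | Group 1 pre/post change |
| Not certified at assignment, so randomized | Literal wording of section 3.0 | Within-group pre/post change in group 2 or group 3 |

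On the third reading, group 2 would also contain PCPs who no longer fit its description as uncertified. No reading separates a new waiver from the other changes between periods.

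**2. How large it could be in group 1**

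Let s be the share of group 1 that is newly waivered (equal numbers of patients per PCP), f the share of their pre-period before the waiver, and m1 and m0 the MAT rates with and without a waiver. Suppose the tool has no effect and the waiver is in force throughout the post period. Then:

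- pre rate = m1 − s × f × (m1 − m0)
- post rate = m1
- apparent rise = s × f × (m1 − m0)

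The SAP gives none of s, f, m1 or m0. It gives a total of 37 to 43 PCPs (section 4.1.1) but no number per group. The values below are assumptions: 12 certified PCPs, k of them newly waivered, m1 = 30%, m0 = 5%, so m1 − m0 = 25 points.

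| k | s = k/12 | Pre rate, f = 0.5 | Rise, f = 0.5 | Pre rate, f = 1 | Rise, f = 1 |
|---|---|---|---|---|---|
| 0 | 0 | 30.0% | 0 | 30.0% | 0 |
| 2 | 0.167 | 27.9% | 2.1 points | 25.8% | 4.2 points |
| 3 | 0.250 | 26.9% | 3.1 points | 23.8% | 6.3 points |
| 4 | 0.333 | 25.8% | 4.2 points | 21.7% | 8.3 points |

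For example, k = 3 and f = 1 gives (9 × 30% + 3 × 5%)/12 = 23.75%, against 30% post.

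Other assumptions move the result widely. With m0 = 0% and m1 = 20%, the rise is 0.10 × 0.5 × 20 = 1.0 point at s = 10% and f = 0.5, and 0.50 × 1 × 20 = 10.0 points at s = 50% and f = 1. With m0 = 5% and m1 = 40%, the same two settings give 1.75 and 17.5 points. A waiver gained part-way through the post period would give a smaller rise.

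**The case against.** The strongest objection is that the SAP never places PCPs with a pending waiver in group 1. Read literally, section 3.0 randomizes anyone uncertified at assignment. This stands, and it is why the point cannot be confined to group 1. It does not remove the problem: a PCP certified between recruitment and assignment still enters group 1 with pre-waiver baseline time, and on the literal reading the mixing moves to groups 2 or 3.

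Two stronger conclusions are tempting, and the documents support neither.

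- A reader might infer that the group 1 MAT rise *will* be due partly to new waivers. The number of such PCPs is not stated and may be zero, and their waiver dates are not given. Nor does the SAP limit MAT to what the PCP prescribes. If MAT obtained through referral counts, the rate before a waiver need not be near zero, and a fall in referral is not certain. Only *can* is supportable.
- A reader might infer that the trial's proof of concept is compromised. Section 1.2 ties proof of concept to acceptability, satisfaction and use rates under Measures 2A to 2C, not to the Secondary Aims. No criterion in the SAP turns on the MAT change.

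It can also be said that this is a descriptive pilot without testing, and that the length of the pre-intervention period may be set in the protocol, which was not available. Both are fair, and the absence of that length from the SAP is not held against it. But a description used to judge usefulness can still mislead, and a pooled group line does so whatever the length of the period.

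**Conclusion.** The point holds as a possible confounder in one descriptive secondary comparison. Where a PCP gains a waiver during or after the pre-intervention period, the pre/post change in MAT use and referral in that PCP's group can reflect the waiver as well as the tool. On the reading suggested by section 2.0 this is group 1, where no certified comparison without access exists. On the literal reading of section 3.0 it is group 2 or 3. The two sections need to be reconciled.

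The size cannot be fixed from the SAP. It is zero if there are no such PCPs, or if none of their pre-period precedes the waiver. With 2 to 4 newly waivered PCPs out of an assumed 12, and assumed MAT rates of 30% and 5%, it is about 2 to 4 percentage points at half the pre-period and 4 to 8 at the whole of it. Measures 2A to 2C are not affected. Severity is minor.

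**What to change.** In the Secondary Aims of section 1.2:

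1. State the date at which certification is determined for grouping, and reconcile sections 2.0 and 3.0 on how PCPs with a pending waiver are classified.
2. Describe group 1 pre/post MAT use and referral for PCPs whose waiver was in force throughout the pre-intervention period.
3. Show PCPs in any group who gain a waiver during or after that period on a separate line for these two outcomes.
4. Keep screening, TAPS use and OUD diagnosis on all PCPs in each group.

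The cost is a few sentences and one waiver date per PCP. The drawback is fewer PCPs in the main group 1 line for MAT and referral. Items 2 to 4 change only the description of results, not who is recruited or assigned.

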3.0 RANDOMIZATION AND FACTORS FOR STRATIFICATION

PCPs who are recruited and are buprenorphine-certified will be placed into the group of PCPs who have OUD-CDS access. PCPs who are recruited and do not have buprenorphine certification will be randomized to receive or not receive access to the OUD-CDS. We will be aware of practice location, patient panel size and number of patients for whom the CDS-OUD was triggered and can analyze results based on individual practice location or panel, but given the small nature of this pilot project we do not anticipate statistically meaningful information from these factors.

4.0 PREDICTION MODELS

Not applicable.

4.1 Rationale for Sample Size and Statistical Power

4.1.1 Projected Number of Sites

This study will occur at PNMG and HPMG, both of which are divisions of HealthPartners. This pilot intervention will occur at primary care clinics at which one or more eligible PCPs have consented to participate. We anticipate a total of 37-43 PCPs from twenty primary care clinics will participate.

4.1.2 Projected Number of Participants per Site

We anticipate 37-43 PCPs from approximately twenty primary care clinics will participate.

4.2 Statistical Methods for Primary and Secondary Outcomes

This pilot study for OUD-CDS feasibility and usability will not have a statistical endpoint. Provider characteristics, patient characteristics, and OUD-CDS use rates will be tracked and described. Pre- and post-intervention surveys of provider confidence in OUD assessment and treatment as well as satisfaction and usability of the OUD-CDS will be described.

4.3 Significance Testing

This pilot study for OUD-CDS feasibility and usability does not entail statistical testing or power calculations. Provider characteristics, patient characteristics, and OUD-CDS use rates will be tracked and described.

4.4 Types of Analyses

Provider characteristics, patient characteristics, and OUD-CDS use rates will be tracked and descriptively analyzed.

4.5 Interim Analysis

Not applicable for a pilot study that will be in the field for 6 months.

4.6 Exploratory Analysis

MAT has been shown to reduce adverse outcomes, such as overdoses, hospitalizations and deaths, for patients with OUD (Mohlman 2016; WHO 2013). As a quality measure to inform future implementation studies of this OUD-CDS, we will collect available EHR data to examine overdoses, ER visits, hospitalizations and deaths for patients with OUD treated by PCPs with and without CDS access. While

this information will likely not be useful for statistical considerations, trends observed could be hypotheses-generating and inform future study needs.

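### Section 4.6 groups the exploratory clinical outcomes by CDS access alone, although every PCP certified at allocation is on the access side, so the tool and certification cannot be told apart

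*SAP*

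**What the plan says.** Four parts of the SAP bear on this point.

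- **Section 4.6 (Exploratory Analysis)** will use EHR data to "examine overdoses, ER visits, hospitalizations and deaths for patients with OUD treated by PCPs with and without CDS access". It does not mention certification. It justifies the analysis by stating that "MAT has been shown to reduce adverse outcomes, such as overdoses, hospitalizations and deaths, for patients with OUD". It adds that the data will probably not support statistical conclusions, but that trends may generate hypotheses and guide later studies.
- **Section 3.0 (Randomization)** sets two allocation rules: "PCPs who are recruited and are buprenorphine-certified will be placed into the group of PCPs who have OUD-CDS access", whereas "PCPs who are recruited and do not have buprenorphine certification will be randomized to receive or not receive access to the OUD-CDS". No randomisation ratio is given.
- **Section 1.2, secondary aims**, divides PCPs into three groups: "1) those with CDS access and buprenorphine certification, (2) PCPs with CDS access but without buprenorphine certification, and (3) PCPs without CDS access". These groups are used for "comparing pre- and post-intervention rates of screening for OUD in high-risk patients, TAPS use, OUD diagnosis, use of medication-assisted therapy" and for referral patterns.
- **Section 2.0 (Recruitment)** states: "We will recruit all PCPs who have or will soon have buprenorphine waivers". Some PCPs may therefore be uncertified at allocation and certified later.

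**The concern.** The access side combines a randomised group (non-certified PCPs given the tool) with a non-randomised one (all the certified PCPs). The no-access side contains only randomised, non-certified PCPs. The two sides therefore differ by design in certification as well as in the tool.

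The SAP's own reasoning makes that difference relevant. It tracks MAT use by certification group in the secondary aims, and in Section 4.6 it links MAT to fewer overdoses, admissions and deaths. Certified PCPs might also see a different mix of OUD patients, but the SAP says nothing about this.

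What is at stake is the use Section 4.6 names for the results, which is to suggest hypotheses for later studies of the tool. A lower or higher event rate on the access side could reflect the tool, certification or both, and a two-way table would not show which. The secondary aims already use a grouping that avoids this, and Section 4.6 neither adopts it nor refers to it.

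**Working it through.** The SAP has no sample-size, power or effect figure for this analysis (Section 4.3 rules out testing and power calculations), so there is nothing to reproduce. The check is the allocation logic, followed by an illustration under stated assumptions.

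**1. Allocation (Section 3.0).**

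| PCP status at allocation | With access | Without access |
|---|---|---|
| Certified | all, by placement | none |
| Not certified | some, by randomisation | the rest, by randomisation |

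Only the second row holds a comparison in which the tool differs and certification does not.

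**2. Spurious difference in a two-way description.** Let w be the share of access-side OUD patients treated by certified PCPs. Let r_cert and r_non be the event rates under certified and non-certified PCPs, and d = r_cert − r_non. If the tool has no effect:

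access − no access = [w·r_cert + (1 − w)·r_non] − r_non = w·d

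The SAP gives neither w nor d. Over an assumed range:

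| w | d = ±5 points | d = ±10 points |
|---|---|---|
| 25% | ±1.25 | ±2.5 |
| 50% | ±2.5 | ±5.0 |
| 75% | ±3.75 | ±7.5 |

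The sign follows d. It could be negative if certification brings more MAT, or positive if certified PCPs treat sicker patients.

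**3. Is that range of w plausible?** Section 4.1.2 states: "We anticipate 37-43 PCPs from approximately twenty primary care clinics will participate". Assume c certified PCPs out of N in total, 1:1 randomisation of the rest, and equal numbers of OUD patients per PCP. Then w = c / [c + (N − c)/2].

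- N = 43, c = 5: w = 5/24 = 21%. With d = ±10 points the spurious difference is ±2.1 points.
- N = 37, c = 20: w = 20/28.5 = 70%. With d = ±10 points it is ±7.0 points.

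If certified PCPs treat more OUD patients each, w is larger.

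**4. The like-for-like contrast.** Comparing non-certified PCPs with and without access removes the w·d term, so the expected difference is 0 when the tool has no effect. Its precision is poor. Assume 12 certified PCPs, which leaves 37 − 12 = 25 to 43 − 12 = 31 non-certified, or about 12 to 16 per arm at 1:1. Assume also 2 to 8 OUD patients per PCP and a 20% event rate. The 95% half-width is 1.96 × √(2 × 0.2 × 0.8 / n), with n patients per arm:

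- n = 12 × 2 = 24: 22.6 points
- n = 14 × 4 = 56: 14.8 points
- n = 16 × 8 = 128: 9.8 points

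These ignore clustering of patients within PCPs, which would normally widen them.

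**The case against.** The strongest reply is that Section 4.6 does not commit to a two-group comparison. It says the events will be examined for patients of both kinds of PCP, which could simply describe whose records are extracted. Where the SAP means to compare, as in the secondary aims, it says so and lists the groups. Those three groups nest within access and no access, so nothing forbids the split. This reading is possible but less natural. Access is the only grouping Section 4.6 names, and trends meant to inform studies of the tool need some contrast.

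The second reply is that little depends on it. There is no statistical endpoint and no test, the study hypothesis concerns feasibility and usability, and Section 4.6 plays down its own data. On the assumed figures, the spurious difference (at most 7.5 points) is smaller than the half-width of the recommended contrast (about 10 to 23 points). This largely stands and is why the point is minor. It does not dispose of it, because leaving out tests does not remove a systematic imbalance, and even a descriptive trend will be attributed to something.

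Third, d could be close to zero, and the figures come almost entirely from assumptions. That also stands. What follows from the SAP alone is that the two influences cannot be separated, not that a distortion of any particular size will occur.

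Finally, the split does not cure everything. Later certification, and the tool changing who is recognised as having OUD, remain as limits even on the randomised contrast.

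**Conclusion.** The concern holds and is minor. By the SAP's own allocation rule, grouping the Section 4.6 outcomes by access alone leaves the tool and certification inseparable, and the SAP itself supplies the link from certification through MAT to most of these outcomes. This rests on the allocation rule and on reading access as the intended grouping, not on any assumed number.

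The size and direction of any distortion cannot be derived from the SAP. The illustrative 1.25 to 7.5 points, in either direction, depends on the assumed values of w and d. The three-group display makes the result interpretable, but with so few PCPs only very large differences would be visible.

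**What to change.** In Section 4.6, replace the grouping by access with the three groups of the secondary aims, classified by certification status at allocation. Name non-certified PCPs with versus without access as the like-for-like descriptive comparison, and show certified PCPs separately as a non-randomised group. Classifying at allocation matters because a PCP who becomes certified later should stay in the group assigned.

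Add one caveat, for example: *The randomised comparison is small, some PCPs may become certified after allocation, and CDS access may itself change who is identified as having OUD; no causal conclusion will be drawn.* Giving the numbers of PCPs and OUD patients beside each rate would help readers but is optional.

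The cost is one or two sentences and a further split of the same EHR extract. The downside is sparser groups, and a main comparison that leaves out the certified PCPs.

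### Does Section 4.6 of the SAP compare events in a group of patients whose membership the decision tool itself can change?

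*SAP*

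**What the plan says.** Section 4.6 (Exploratory Analysis) states that "we will collect available EHR data to examine overdoses" and other serious events. The population is described only as patients with OUD, split by whether their PCP had the tool: "overdoses, ER visits, hospitalizations and deaths for patients with OUD treated by PCPs with and without CDS access". It gives no date or rule for establishing OUD status. It adds that "this information will likely not be useful for statistical considerations", and that "trends observed could be hypotheses-generating and inform future study needs".

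The Secondary Aims in Section 1.2 judge usefulness by "comparing pre- and post-intervention rates of screening for OUD in high-risk patients, TAPS use, OUD diagnosis, use of medication-assisted therapy" and by referral patterns, in three groups of PCPs, one of which has no access to the tool.

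On allocation, Section 3.0 says that "PCPs who are recruited and are buprenorphine-certified will be placed into the group of PCPs who have OUD-CDS access". Only PCPs without certification are randomized.

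Sections 4.2 to 4.4 make the whole analysis descriptive, with no testing and no power calculation.

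**The concern.** One section treats OUD diagnosis as something the tool may alter. Another uses OUD status to decide whose events are counted, and then sets PCPs with access against PCPs without it. If status is read from diagnoses recorded after go-live, the comparison conditions on a possible consequence of the intervention. A tool that finds more cases, and milder ones, would then seem to lower event rates. One that finds more severe cases would seem to raise them. Neither pattern needs any effect on a patient.

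What is at stake is the use Section 4.6 names for these trends, which is planning later work. A trend produced by case-finding could point a future study in the wrong direction. Measures 1 and 2A to 2C do not use this population and are untouched.

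**Working it through.** The SAP gives no event count, denominator or effect measure for Section 4.6, so there is no figure to reproduce. The check asks whether the mechanism works, how large it could be, and what a different cohort would gain. All inputs below are assumptions.

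**1. Mechanism.** Take 40 patients per group with OUD recorded before go-live, at 30% event risk (12 expected events), and no effect of the tool. Let *a* and *b* be the new diagnoses with and without access, and *r* the risk in new cases.

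Apparent ratio = [(12 + a·r)/(40 + a)] ÷ [(12 + b·r)/(40 + b)]

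| a, b | r | With access | Without access | Ratio |
|---|---|---|---|---|
| 20, 10 | 0.10 | 14/60 | 13/50 | 0.90 |
| 20, 10 | 0.20 | 16/60 | 14/50 | 0.95 |
| 20, 10 | 0.30 | 18/60 | 15/50 | 1.00 |
| 20, 10 | 0.40 | 20/60 | 16/50 | 1.04 |
| 40, 10 | 0.10 | 16/80 | 13/50 | 0.77 |
| 40, 10 | 0.20 | 20/80 | 14/50 | 0.89 |
| 40, 10 | 0.30 | 24/80 | 15/50 | 1.00 |
| 40, 10 | 0.40 | 28/80 | 16/50 | 1.09 |

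With a = b = 10 the ratio is 1.00 at every *r*. A spurious trend therefore needs both unequal case-finding and unequal risk between new and earlier cases.

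A second set of inputs has 40 earlier cases per group, 5 new without access and 30 with it:
- Earlier risk 0.20, new risk 0.05: (8 + 1.5)/70 = 0.136 against (8 + 0.25)/45 = 0.183, ratio 0.74.
- Earlier risk 0.10, new risk 0.20: (4 + 6)/70 = 0.143 against (4 + 1)/45 = 0.111, ratio 1.29.

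So the artefact can run either way.

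**2. Size against noise.** The 95% interval on the log scale uses SE = √(1/x₁ − 1/n₁ + 1/x₂ − 1/n₂), ignoring clustering by PCP.
- 16/80 against 13/50: SE = √(0.0625 − 0.0125 + 0.0769 − 0.0200) = 0.327. The ratio is 0.77, interval 0.41 to 1.46.
- 28/80 against 16/50: SE = √(0.0357 − 0.0125 + 0.0625 − 0.0200) = 0.256. The ratio is 1.09, interval 0.66 to 1.81.

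Both intervals comfortably include 1.

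**3. What fixing OUD status before go-live would gain.** With equal baseline risk the ratio returns to 0.30/0.30 = 1.00. But every certified PCP has access without randomization, so the groups need not start equal. If baseline risk with access were 25% or 35% against 30% without, the ratio would be 0.25/0.30 = 0.83 or 0.35/0.30 = 1.17. That residual is about as large as the artefact removed.

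**The case for a change.** The strongest case for a change is that noise and bias are different faults. The caveat in Section 4.6 warns of limited statistical usefulness, not of a population that depends on access. Since nothing is tested, the descriptive trend is the whole output, and who is counted decides what it means. If a later, larger study copied the definition, the noise would shrink and the bias would not. Stating the timing and listing new diagnoses separately would take a sentence or two.

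Part of this stands. The SAP is silent on timing, and an analyst should report when OUD status was established. A table that separates earlier from new diagnoses would be easier to read.

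It does not carry the case for amending the plan, for three reasons:
- The fault depends on a choice the SAP does not make. How OUD is identified in EHR data is a cohort definition that the protocol, not available for this review, may already hold.
- The Secondary Aims already report diagnosis rates before and after by PCP group, including PCPs without access. A reader would see unequal case-finding, the condition the artefact needs, although events would not be split by it.
- The alternatives have costs. A pre-go-live cohort is smaller and drops from the main display the newly identified patients. An all-high-risk cohort includes patients without OUD and dilutes any effect. For an exploratory quality measure, all patients with OUD under care is a defensible population.

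**Conclusion.** The concern is sound as a mechanism but shows no error in the plan. It describes an unstated detail in an exploratory paragraph that plans no ratio or test and claims only to suggest hypotheses. Followed as written, the SAP does not commit anyone to a wrong result.

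Under the assumed inputs the spurious ratio lies between 0.74 and 1.29. In the two examples where an interval was computed, the artefact is well within sampling error. Confounding of access with certification could leave 0.83 or 1.17 after any redefinition of the cohort, so the contrast by access could not be read as an effect of the tool in either case. These sizes rest wholly on assumed counts and risks, since the SAP supplies none.

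This is a gap that analysts can fill sensibly when they write the EHR query and label the table. Measures 1 and 2A to 2C are unaffected, and no change is needed.
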